CHECKLIST FOR PATIENT ELIGIBILITY AND NECESSARY INFORMATION: CHARMS

PATIENT ID		PATIENT NAME	
YES	NO	VALUE/DATE	
Any "NO" answers will make a patient ineligible for study participation.			
			Received prior myeloablative or non-myeloablative allogeneic hematopoietic stem cell transplant using bone marrow, single or double cord blood, or PBSC
			Cells Administered as treatment for; Persistent or relapsed CMV, adenovirus, EBV, HHV6 or BK virus (single or multiple) infections despite standard therapy(defined in section 2.3.1) OR Progressive or persistent JC virus infection (defined in section 2.3.1) Patients with multiple CMV, EBV, Adenovirus, HHV6 and BK virus infections are eligible given that each infection is persistent despite standard therapy as defined above. Patients with multiple infections with one or more reactivation and one or more controlled infection are eligible to enroll.
			Steroids less or equal to 0.5 mg/kg/day prednisone (or equivalent)
			HgB>8.0
			Pulse oximetry of >90% on room air
			Available multivirus-specific T lymphocyte lines
			Negative pregnancy test (if applicable)
			Patient or parent/guardian capable of providing informed consent
Any "YES" answers will make a patient ineligible for study participation.			
			Received ATG, Campath or other T cell immunosuppressive monoclonal antibodies in the last 28 days of screening for enrollment
			Patients with other uncontrolled infections (see 2.3.2 for definitions)
			Patients who are less than 28 days removed from their allogeneic hematopoietic stem cell transplant or who have received donor lymphocyte infusions (DLI) within 28 days.
			Evidence of active acute GVHD \geq grade 2
			Active and uncontrolled relapse of malignancy

Signature of MD _____

Date _____

CHARMS Protocol v1.0 (10.30.13)
Version 2.0 (12.09.13)
Version 2.1 (03.07.14)
Version 3.0 (06.17.14)
Version 4.0 (11.06.14)

Version 5.0 (10.6.15)
Version 6.0 (08.29.16)
Version 7.0 (04.26.17)
Version 8.0 (05.24.17)
Version 9.0 (08.10.17)

PROTOCOL SYNOPSIS

Administration of Most Closely HLA-Matched Multivirus-Specific Cytotoxic T-Lymphocytes for the Treatment of EBV, CMV, Adenovirus, HHV6, and BK virus Infections post Allogeneic Stem Cell Transplant

Study Design:

The primary purpose of the study is to evaluate whether most closely HLA-matched multivirus-specific T cell lines obtained from a bank of allogeneic virus-specific T cell lines (VSTs) have antiviral activity against five viruses: BK virus, HHV6, EBV, CMV and adenovirus.

Reconstitution of anti-viral immunity by donor-derived VSTs has shown promise in preventing and treating infections associated with CMV, EBV and adenovirus post-transplant. More recently, an ongoing phase I/II study at our institution indicates that this approach can be extended to include additional viruses including BK virus and HHV6. However, the time taken to prepare patient-specific products and lack of virus-specific memory T cells in cord blood and seronegative donors, limits their value.

An alternative is to use banked partially HLA-matched allogeneic VSTs. A prior phase II study at our institution using trivirus-specific VSTs generated using monocytes and EBV-transformed B cells gene-modified with a clinical grade adenoviral vector expressing CMV-pp65 to activate and expand specific T cells showed the feasibility, safety and activity of this approach for the treatment of refractory CMV, EBV and Adenovirus infections. However, the production process was lengthy, requiring 8-12 weeks, with exposure to biohazards (B95.8 EBV viral strain and adenovector), while antigenic competition between different viral components precluded increasing the spectrum of specificity beyond these three viruses.

We have overcome these limitations and in the current trial, we will evaluate whether rapidly generated, allogeneic most closely HLA-matched multivirus-specific VSTs, activated using overlapping peptide libraries spanning immunogenic antigens from BK virus, HHV6, CMV, adenovirus and EBV will be safe and produce antiviral effects in allogeneic HSCT recipients infected with one of more of the targeted viruses that are persistent despite conventional antiviral therapy. The study agent will be assessed for safety (stopping rules defined) and antiviral activity.

Primary Objective:

The primary objective of this pilot study is to determine the feasibility and safety of administering partially HLA-matched VSTs specific for five viruses in HSCT recipients with persistent viral reactivations or

CHARMS Protocol v1.0 (10.30.13)	Version 5.0 (10.6.15)
Version 2.0 (12.09.13)	Version 6.0 (08.29.16)
Version 2.1 (03.07.14)	Version 7.0 (04.26.17)
Version 3.0 (06.17.14)	Version 8.0 (05.24.17)
Version 4.0 (11.06.14)	Version 9.0 (08.10.17)

infections. Patients will be closely monitored for any possible association between VST infusion and GVHD.

Secondary Objectives: Secondary objectives are to determine: effects of partially HLA-matched VST infusion on viral load and viral reactivations within 12 months, reconstitution of antiviral immunity, persistence of infused partially HLA-matched VSTs and effects on viral clinical signs and symptoms. Additional endpoints include secondary graft failure, development of chronic GVHD, clinical response to VST infusions, effects of HLA matching with clinical response and overall survival.

Eligibility: Patients will be eligible following any type of allogeneic transplant if they have BK virus, HHV6, CMV, adenovirus and/or EBV infection persistent despite standard therapy (as defined in section 2.3). In addition patients with progressive or persistent JC virus infection (which is highly homologous to BK virus) may also be enrolled. If patients are receiving steroids for treatment of GVHD or for other reasons, dosage must have been tapered to 0.5 mg/kg/day Prednisone (or equivalent) prior to study enrollment. Patients may not have received ATG, or Campath or other immunosuppressive monoclonal antibodies in the last 28 days.

Treatment Description: The treatment schedule is as follows:
Patients will receive 2×10^7 partially HLA-matched VSTs/m² as a single infusion. In the rare case where insufficient banked cell product is available, a lower number of cells may be infused after discussion with the principal investigator, patient and/or guardian and the treatment team. If they have a partial response (as defined by a 50% fall in viral load) they are eligible to receive up to 4 additional doses from day 28 after the initial infusion and at 2 weekly intervals thereafter. The viral load of the virus (or viruses) that patients are initially treated for must be monitored by viral PCR. GVHD scores will be recorded at the intervals defined.

Accrual Objective: A maximum of 80 patients will receive at least one infusion of VSTs.

Accrual Period: The estimated accrual period is 4 years.

Study Duration: Patients will be followed for toxicity for 28 days, acute GVHD for 6 weeks; anti-viral responses for up to 12 months and long term follow up including chronic GVHD for 12 months following the final VST infusion.

STUDY SCHEMA

Aim: To determine whether partially HLA-matched VSTs are safe and have antiviral activity against EBV, CMV, Adenovirus, HHV6 and BK virus.

Inclusion Criteria	Exclusion Criteria

 1) Received prior myeloablative or non-myeloablative allogeneic hematopoietic stem cell transplant using either bone marrow, single/double cord blood or PBSC 2) Cells administered as; 
 a) Treatment of relapsed or persistent reactivation or infection for EBV, CMV, Adenovirus, HHV6 and/or BK virus despite standard therapy. Multiple infections are eligible to enroll. b) Early treatment for single or multiple infections with EBV, CMV, adenovirus, HHV6 and/or BK virus following treatment failure or unable to tolerate standard therapy c) Treatment of progressive or persistent JC virus infection 3) Steroids less or equal to 0.5 mg/kg/day prednisone 4) Hgb>8.0 5) Pulse oximetry of > 90% on room air 6) Available VSTs 7) Negative pregnancy test (if female of childbearing potential after reduced intensity conditioning) 8) Patient or parent/guardian capable of providing informed consent. 	
 1) Received ATG, Campath or other T cell immunosuppressive monoclonal antibodies in the last 28 days. 2) Patients with other uncontrolled infections (see 2.3.2 for definitions) 3) Patients who are less than 28 days removed from their allogeneic hematopoietic stem cell transplant or who have received donor lymphocyte infusions (DLI) within 28 days. 4) Evidence of GVHD \geq grade 2 5) Active and uncontrolled relapse of malignancy

Up to 4 additional doses can be administered from day 28 after the initial infusion if a partial response is obtained and patient meets eligibility criteria for subsequent infusions. Subsequent doses should be at least 14 days apart.

CHARMS Protocol v1.0 (10.30.13)
Version 2.0 (12.09.13)
Version 2.1 (03.07.14)
Version 3.0 (06.17.14)
Version 4.0 (11.06.14)

Version 5.0 (10.6.15)
Version 6.0 (08.29.16)
Version 7.0 (04.26.17)
Version 8.0 (05.24.17)
Version 9.0 (08.10.17)

Primary endpoints:

- Feasibility of finding a suitable line
- Safety including acute GVHD grades III-IV within 42 days of the last dose of VSTs or grades 3-5 non-hematological adverse events within 28 days of the last VST dose and that are not due to the pre-existing infection or the original malignancy or pre-existing co-morbidities as defined by the NCI Common Terminology Criteria for Adverse Events (CTCAE), Version 4.X.

Secondary Endpoints

- Antiviral responses 42 days after the first dose of VSTs
- Effects of partially HLA-matched VSTs on viral loads
- Persistence of partially HLA-matched VSTs and effects on clinical signs/symptoms
- Reconstitution of antiviral immunity at 1, 2, 3, 4,6 weeks and 3 months
- Viral reactivations within 12 months
- Secondary graft failure at 30 days
- Chronic GVHD at 3 months, 6 months and 12 months
- Clinical response to VST infusions at 6 weeks and 3 months
- Effects of HLA matching
- Effects of choosing a line with confirmed antiviral activity through one or more shared alleles
- Overall survival at 3 months, 6 months and 12 months

CHARMS Protocol v1.0 (10.30.13)	Version 5.0 (10.6.15)
Version 2.0 (12.09.13)	Version 6.0 (08.29.16)
Version 2.1 (03.07.14)	Version 7.0 (04.26.17)
Version 3.0 (06.17.14)	Version 8.0 (05.24.17)
Version 4.0 (11.06.14)	Version 9.0 (08.10.17)

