2.4.1.4 Criteria for Selection of VST Line

In general preference will be assigned to the infusion of a line with confirmed virus-specific activity against the infecting virus through a shared HLA allele rather than the overall level of HLA match. For example for a patient with an adenovirus infection a line that matches at 2 loci but that has recognition of adenovirus mediated through those antigens would be preferable to a line matched at 3 loci but with no demonstrated activity against adenovirus. Patients with a partial response are eligible to receive up to 4 additional doses.

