5 STATISTICAL CONSIDERATIONS

5.1 Study Design Synopsis

This study is designed as a single-arm pilot study to evaluate the feasibility, safety and efficacy of most closely HLA matched multivirus specific VST lines (CHM-VSTs) in HSCT patients with either of five viruses; BK virus, HHV6, EBV, CMV and adenovirus persistent despite of standard therapy. The study first conducts a phase IIA trial to evaluate the clinical response rate. After the phase IIA trial, if the data suggests excellent clinical responses that warrant further investigation, the study will be expanded to recruit 30 additional patients to evaluate the role of HLA matching on viral outcomes.

The total sample size of the study will be a maximum of 80 patients who receive at least one VST infusion. The sample size for the phase II A trial is 50 patients who receive at least one VST infusion. A larger number of potential subjects will be screened to assess the feasibility of the approach.

CHARMS Protocol v1.0 (10.30.13)	Version 5.0 (10.6.15)
Version 2.0 (12.09.13)	Version 6.0 (08.29.16)
Version 2.1 (03.07.14)	Version 7.0 (04.26.17)
Version 3.0 (06.17.14)	Version 8.0 (05.24.17)
Version 4.0 (11.06.14)	Version 9.0 (08.10.17)

We expect to enroll 15-20 patients per year and therefore expect the study to conclude within the estimated accrual period of 4 years.

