5.2 Sample Size Determination and Design Characteristics

Frist, the study will conduct a single arm pilot study using a phase IIa design. Simon's two-stage Minimax design⁶⁰ will be used to for the single-arm pilot study. Under the null hypothesis that the VST is not active, the data from previous trials suggest that the true response rate is 20% in anti-viral activity, where a positive response is defined as the viral load reduction to the normal level for at least one of the 5 virus types (CMV, EBV, adenovirus, BK virus and HHV6) within 42 days following the initial treatment of VST.

Allowing a 5% type-I error and 90% power, the null hypothesis will be tested against a one-sided alternative that the true response rate is 40%. The maximum size is 45 eligible patients, defined as the patients who receive the VST infusion and who can finish the 42 days follow-up. We anticipate that most patients will finish the follow up and will allow a 10% drop out rate. Therefore, the maximum sample size is 50.

The phase IIa trial operates in two stages, where the first stage recruits 24 patients. The trial pauses at the end of the first stage to make the decision on whether to stop the trial early due to lack of enough efficacy for treating viral infection, according to the rule as follows. Of the 24 patients at the first stage, if 5 or fewer positive responses are observed, then the study will be stopped. Otherwise, 21 additional patients will be accrued to reach the goal of 45 accruals. At the end of the trial, the null hypothesis will be rejected, if 14 or more positive responses are observed in among the 45 patients. This design has 65.6% chance to stop early when the true response rate is 20%.

After the phase IIa trial suggests excellent clinical responses that warrant further investigation, the study will be expanded to recruit 30 additional patients to evaluate the viral reduction based HLA matching. We hypothesize the viral reduction among the low HLA matching group (1/8, 2/8, or 3/8 HLA matching) is not worse than the high HLA matching group (4/8, 5/8, 6/8, 7/8, or 8/8).

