The sample size is calculated based on non-inferiority trial for comparing two-sample means. Based on the preliminary data, the standard deviation of viral reduction is about 18. We assume that the viral reduction in the low HLA matching group is not inferior to the high HLA matching group when the difference in the viral reduction between the two groups is no less than -10 (non-inferiority margin). Preliminary data suggest that the ratio of sample size between the low and high HLA matching groups is 5 to 7. A sample size of 30 patients with low HLA matching and 42 with high HLA match (total 72) would have at least 85% power to test the non-inferiority hypothesis with 2-side 5% alpha level. Assuming 10% of patients to be lost to follow-up, then the study will recruit up to a total of 80 patients.

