5.4 Data Analysis

Safety and toxicity outcomes including adverse events, GvHD, clinical signs of viral infections, secondary graft failure and laboratory measurements will be summarized using descriptive statistics (frequency table, means, standard deviations, medians and ranges). Toxicity information including the type, severity, time of onset, time of resolution, and the probable association with the study regimen will be tabulated and summarized.

Response rate including complete response, partial response and mixed response will be summarized as frequency table. The response rate with 95% CI will be reported. Reconstitution of antiviral immunity using multimer analysis and ELISpot assays will also be summarized using descriptive statistics at each time point. Pairwise comparisons will be performed to compare changes of these immunological parameters from VST infusion to each time point of post-infusion measurements using paired t-tests or Wilcoxon signed-ranks tests. The normality assumption will

CHARMS Protocol v1.0 (10.30.13)	Version 5.0 (10.6.15)
Version 2.0 (12.09.13)	Version 6.0 (08.29.16)
Version 2.1 (03.07.14)	Version 7.0 (04.26.17)
Version 3.0 (06.17.14)	Version 8.0 (05.24.17)
Version 4.0 (11.06.14)	Version 9.0 (08.10.17)

be assessed and transformations to achieve approximate normality will be carried out if necessary. Overall survival post VST infusion will be analyzed by the Kaplan-Meier method.

Viral load reduction will be compared between the low and high HLA using the two-sample t-test. Additionally, Viral load levels will be correlated with immunological parameters using correlation coefficients. Longitudinal analysis is employed to model repeatedly-measured immunologic parameters. This will allow us to model patterns of immune response per patient while allowing for varying intercepts and slopes for a patient. Viral load levels will be correlated with immunological parameters using correlation coefficients. These modeling strategies will be considered exploratory in nature due to the limited patient numbers in this initial trial.

Overall survival since allogeneic hematopoietic stem cell transplant will be analyzed using the Kaplan-Meier method. Cumulative incidences to the time of complete/partial resolution of viral infection and viral load reduction, considering death a competing event, will be analyzed in univariate and multivariate model using the Fine and Gray method.

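### The endpoint of HLA matching on clinical response has no named analysis, and confirmed line activity, which drives line choice and may confound match level, is not analysed at all

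*Combined protocol and SAP*

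**What the plan says.** Endpoints. The synopsis, under Secondary Objectives, includes "effects of HLA matching with clinical response and overall survival". The Study Schema's list of secondary endpoints shortens this to "Effects of HLA matching" and adds a separate item: "Effects of choosing a line with confirmed antiviral activity through one or more shared alleles".

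Purpose and hypothesis. Section 5.1 says that "the study will be expanded to recruit 30 additional patients to evaluate the role of HLA matching on viral outcomes". Section 5.2 puts this in terms of viral reduction: "We hypothesize the viral reduction among the low HLA matching group (1/8, 2/8, or 3/8 HLA matching) is not worse than the high HLA matching". High match there means 4/8 to 8/8. The size calculation there is a non-inferiority comparison of two means with SD about 18, margin -10, 30 low-match and 42 high-match patients, two-sided 5% and at least 85% power. No unit is given for the SD or the margin.

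Analysis. Section 5.4 says: "Viral load reduction will be compared between the low and high HLA using the two-sample t-test". It gives no margin, time point or adjustment. Response (complete, partial and mixed) is a frequency table with a 95% CI, not split by match. Time to complete or partial resolution goes into univariate and multivariate Fine and Gray models, with no covariates named. Section 5 does not mention confirmed activity.

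Line choice. Section 2.4.1.4 says that "preference will be assigned to the infusion of a line with confirmed virus-specific activity against the infecting virus through a shared HLA allele" ahead of overall match.

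**The concern.** There are three linked gaps.

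- **Response by match.** The synopsis asks how matching relates to clinical response. Section 5 specifies a test for a different quantity and leaves response unsplit.
- **Confounding.** Match level is not assigned at random. A low-match line may be infused precisely because its activity against the infecting virus is confirmed, and a high-match line may be used without such confirmation. The t-test then mixes the effect of match with the effect of confirmed activity. The factor that could separate the two is a listed endpoint with no analysis.
- **Mean versus threshold.** Response in 5.2 is a return to normal within 42 days. Section 3.1.2 defines complete response by the normal range together with signs and symptoms, and partial response by a 50% change. Similar means need not imply similar proportions past a threshold.

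At stake is what the expansion can conclude. A finding that low match is not worse on mean reduction would carry no responder figures beside it and no account of how the lines were picked.

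**Working it through.** **1. The plan's own figure.** Inputs from 5.2: SD 18, margin 10, groups of 30 and 42. SE = 18 × √(1/30 + 1/42) = 4.30. With true difference 0, power = Φ(10/4.30 − 1.96) = 64.2% at two-sided 5%, and 75.1% at one-sided 5%. The stated 85% does not reproduce. That is a separate matter; it is shown because the same SE is used below.

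**2. What the mean test lets through under a normal model.** Non-inferiority requires the lower 95% limit to exceed -10, so the observed difference must exceed −10 + 1.96 × 4.30 = −1.6. At a true deficit of 10 the chance of passing is 2.5%; at a true deficit of 5 it is about 20%. To translate into response, assume percentage points and a high-match rate of 74% (complete or partial response in the prior trivirus study, section 1.10). The low-match rate is then Φ(z(0.74) − 10/18) = 53.5% at a deficit of 10, and Φ(z(0.74) − 5/18) = 64.3% at a deficit of 5.

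**3. What it lets through under a capped percent scale (assumed).** Let 10% of each group fall by 40%. Of the rest, complete responders fall by 100% and the others by 95%.

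| | Low match | High match |
|---|---|---|
| Normalise | 27% | 63% |
| Fall 95% | 63% | 27% |
| Fall 40% | 10% | 10% |
| Mean fall | 27 + 59.85 + 4 = 90.85 | 63 + 25.65 + 4 = 92.65 |
| SD | about 17 | about 18 |

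The means differ by −1.8 and the SDs are close to the plan's 18. In simulation at 30 versus 42, low match is declared non-inferior in about 52% of runs, although normalisation differs by 36 points. Falls of at least 50% are 90% in both groups, so the hidden gap lies in normalisation only. A different assumed shape, with falls of at least 50% in 70% of low-match and 100% of high-match patients, passes in 57% of runs.

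**4. Confounding.** If confirmed activity changes mean reduction by δ in both groups, the unadjusted difference is shifted by (share confirmed in low match − share confirmed in high match) × δ. The documents give neither share nor δ, so size and direction are unknown.

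**5. What a response comparison can deliver.** The 95% half-width for a difference at a 40% rate (the 5.2 alternative) is 1.96 × √(0.24/n₁ + 0.24/n₂):
- match, 30 and 42: ±23.0 points
- confirmed status, assumed 36:36: ±22.6 points
- confirmed status, assumed 58:14: ±28.6 points

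At 40%, 72 patients give 0.40 × 72 ≈ 29 responders, enough for a two-factor exploratory model but not for a powered test.

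**The case against.** The best defence has four parts.

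- **The t-test fits the aim as sections 5.1 and 5.2 word it.** The expansion is about viral outcomes, and only the synopsis ties matching to clinical response. This is true and makes the mismatch softer. It does not supply the analysis that the synopsis calls for.
- **The Fine and Gray model is response-based and could carry HLA match.** This also stands: it would be wrong to infer that 5.4 has no route to a response analysis. But no covariate is named, so the route is left open rather than specified.
- **The mean test is not lenient.** A reader might infer that any difference inside -10 passes, for example a uniform 92% fall against a uniform 100% fall, and so that low match could be accepted with no normalisation against full normalisation. The documents do not support this. That example has zero variance. With the plan's SD, an observed −8 has a lower limit of −8 − 1.96 × 4.30 = −16.4 and fails. A 92% fall is also at least a partial response under 3.1.2.
- **This is a pilot, and the added intervals are wide.** That is correct, and it is why the request is for estimates and not for a new test.

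A reader might also infer, from the future tense used for epitope mapping in 2.4.1.1, that confirmed status could be settled after response is known. Section 2.4.1.4 uses that status to choose the line, so the status used for selection must exist before infusion. The inference is speculative.

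**Conclusion.** Three things follow from the text alone: response is not analysed by match, the confirmed-activity endpoint has no analysis, and the one HLA comparison is unadjusted although line choice favours confirmed activity. That the comparison may be confounded follows from the selection rule; the size and direction cannot be derived.

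That a mean-based finding of not worse can hide a responder gap is conditional. It needs a skewed or capped scale, which is plausible for percent falls but is an assumption. The 36-point gap in normalisation that passed about half the time is an illustration, not an estimate for this trial. Under the normal model with SD 18, a true deficit at the margin passes only 2.5% of the time. The documents therefore do not support saying that the plan would accept low match with a far lower response rate.

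The point is worth acting on because the repair is cheap and answers endpoints that the plan already lists.

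**What to change.** In section 5.4:

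1. Report response within 42 days by low versus high match, using both the 5.2 definition and the complete/partial definition in 3.1.2, with the difference and 95% CI, beside the viral load comparison. State the unit and time point of viral reduction, and interpret any conclusion of not worse together with the responder difference.
2. Give the same table for lines with and without confirmed activity through a shared allele. Cross-tabulate match by confirmed status first, since adjustment is informative only if both kinds of line occur in both match groups.
3. Fit one exploratory response model with match level and confirmed status, both as recorded at line selection before infusion. It can be logistic, or the planned Fine and Gray model with these two covariates named.

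The cost is analysis wording, two tables and one model on data already collected, with no change to line selection or sample size. The downside is imprecision, about ±23 to ±29 points, so the results should be labelled exploratory.
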